the hemodialysis population will be compared with that of the Austrian general population. Adjusted hazard ratios for the male-to-female mortality risk in hemodialysis patients, by region will be performed using Cox regression analysis. Statistical modeling will closely follow a previously published study of hemodialysis data, analyzed by sex and country/region.⁴ All obtained p-values will be considered exploratory in nature.

2.2 Description and analysis of sex-specific differences in treatment and outcomes in patients with chronic kidney disease.

Hypothesis:

There are sex-specific differences in treatment, length of hospitalization, mortality and dialysis initiation in patients with chronic kidney disease admitted to internal medicine wards.

Methodology:

Patients hospitalized at internal medicine wards of the Krankenanstaltsverbund (KAV) between Jan 1st 2015 and Dec 31st 2015 with eGFR <60 mL/min/1.73m will be included.

Primary study endpoints are length of hospital stay, death within hospitalization and dialysis initiation. Secondary endpoints are renal function parameters (eGFR, serum creatinine, blood urea nitrogen) and proteinuria during hospital stay. Laboratory data will be extracted from the KAV laboratory database and patient characteristics will be derived from the KAV patient management database.

Statistics:

Descriptive statistics will be used for presentation of demographic and clinical patient characteristics and prevalence of chronic kidney disease in women as compared to men.

Further statistical methods will be chosen according to data availability and quality: The present plans include logistic regression to calculate the male-to-female odds of reaching one of the endpoints, conditional logistic regression for pair-matched data or logistic regression with propensity scoring.

2.3 Descriptive analysis of decision-making by doctors and patients with regards to renal replacement therapy initiation

Hypothesis

There are sex-specific differences in decision-making of doctors and patients with end-stage renal disease with regards to renal replacement therapy initiation.

Methodology

Questionnaires will be sent to every Austrian chronic kidney disease outpatient clinic willing to participate. Doctors and patients will complete the questionnaire anonymously and questionnaires will be sent back after a 3 months-time period of data collection /questionnaire completion.

The following questions will be included in the questionnaire:

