Doctor level:

In your chronic kidney disease clinic

1. How many men (a) and how many women (b) were registered in the year 2016?
2. According to the first lab result that was taken in 2016, how many men (a) and how many women (b) were in chronic kidney disease stage 4, 3a, 3b, and 2?
3. How many times did the registered men (a) and the registered women (b) have their labs checked and saw the doctor during the year 2016? Please subdivide also by chronic kidney disease stage.
4. How many men (a) and how many women (b) have you informed they will likely need renal replacement therapy (RRT) in the next 12 months?
5. How many men (a) and how many women (b) already have a fistula, and how many have a graft for vascular access?
6. How many men (a) and how many women (b) have you informed about preemptive transplantation as an option for RRT?
7. How many men (a) and how many women (b) have you informed about peritoneal dialysis as an option for RRT?
8. How many men (a) and how many women (b) have you informed about hemodialysis as an option for RRT?
9. How many men (a) and how many women (b) ended up on RRT (HD, PD or preemptive transplantation) during the year 2016?
10. How many men (a) and how many women (b) did you consider end stage and thus in need of undergoing RRT in 2016?
11. How many men (a) and how many women (b) refused RRT in 2016 despite your advice?
12. Among those whom you considered end stage in the year 2016, in how many men (a) and how many women (b) was the decision to withhold or not do RRT mutual (taken by doctor and patient together)?
13. How many men (a) and how many women (b) started RRT in 2016 against your advice?
14. How would you judge your own decision making regarding RRT initiation
 - a) Influenced by patient sex, with men more likely to start RRT
 - b) Influenced by patient sex, with women more likely to start RRT
 - c) Not influenced by patient sex

To obtain adequate data, a reimbursement based on the number of patients seen by the center will be offered to the medical director of the outpatient clinic in December 2016. A specific plan on how to arrive at answering the questions correctly must be submitted; in principle, this plan should encompass several meetings with the outpatient clinic doctors in early 2017, in order to obtain an answer from all of them together (only question 14 must be individually answered).

Patient level:

1. I am a man (a), a woman (b).
2. My age is ... years.

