3. My nationality is Austrian (a), Non-Austrian (b).
4. My native language is German (a), not German (b).
5. I am married (a), living with my partner (b), separated or divorced (c), single (d), widowed (e).
6. My highest level of education is less than high school.
7. I know the reason (a), don't know the reason (b) why my kidneys are weak or failing.
8. The most important reason why my kidneys are weak or failing, to the best of my knowledge is hypertension (a), diabetes (b), glomerulonephritis (c), polycystic kidney disease (d); another reason not mentioned here (e).
9. I come to the clinic seldom [once a year at the most] (a), frequently [at least 3 times a year] (b) in order to check my labs and/or discuss treatment and progression of my disease.
10. A doctor at this clinic has told me (a) has not told me (b) that I will likely need renal replacement therapy (RRT) within the next 12 months.
11. I already have (a) / don't yet have (b) a fistula or graft for vascular hemodialysis access.
12. A doctor at this clinic has informed me (a) has not informed me (b) about the possibility to undergo pre-emptive transplantation as an option for RRT.
13. A doctor at this clinic has informed me (a) has not informed me (b) about peritoneal dialysis as an option for RRT.
14. A doctor at this clinic has informed me (a) has not informed me (b) about the possibility to undergo hemodialysis as an option for RRT.
 1. I consider myself end stage and thus in need of undergoing RRT within the next 12 months.
15. RRT is not an option for me. I would rather die than go on dialysis.
16. I suffer from nausea/vomiting (a), fatigue/tiredness (b), edema (c), dyspnea (d).
17. I can take care (a), cannot take care (b) of my household.

Methodological Note: The questionnaire will be handed out to all patients coming to the outpatient clinic in the year 2017 by non-medical (administrative) personnel. The number of returned questionnaires will be counted and compared to the number of questionnaires that was handed out. Only the sex of the patient receiving the questionnaire will be recorded. The return of the questionnaire will be anonymous, by placing a box in the patient waiting area.

Statistics:

Data will be entered into an IBM SPSS statistics database. Descriptive analysis and graphical illustrations will be performed.

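### Patient item 15, the only patient-reported refusal item, joins refusing all renal replacement therapy with preferring death to dialysis, so a patient open to transplant but not dialysis cannot answer it accurately

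*Combined protocol and SAP*

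**What the plan says.** Sub-study 3 is a questionnaire survey of doctors and patients. Its hypothesis in section 2.3 is: "There are sex-specific differences in decision-making of doctors and patients with end-stage renal disease with regards to renal replacement therapy initiation".

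- **Patient item 15:** "RRT is not an option for me. I would rather die than go on dialysis". These are two sentences under one item number. No (a)/(b) options are printed, unlike items 10 to 14 and 17.
- **Scope of RRT, patient form:** item 12, three items earlier, asks whether a doctor has informed the patient "about the possibility to undergo pre-emptive transplantation as an option for RRT".
- **Scope of RRT, doctor form:** question 9 asks how many men and women "ended up on RRT (HD, PD or preemptive transplantation) during the year 2016".
- **Refusal on the doctor form:** question 11 asks how many men and women "refused RRT in 2016 despite your advice". Question 12 asks, for patients considered end stage, in how many men and women "was the decision to withhold or not do RRT mutual (taken by doctor and patient together").
- **Return of the patient form:** "The return of the questionnaire will be anonymous, by placing a box in the patient waiting area".
- **Analysis:** "Descriptive analysis and graphical illustrations will be performed". No scoring rule is given for item 15.

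**The concern.** Item 15 asks two questions at once. The first sentence rules out RRT as a whole; the second rules out dialysis and adds a statement about dying. On the survey's own use of RRT these are not equivalent, because transplantation belongs to the first and not to the second.

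Two groups have no accurate answer. One is patients who reject dialysis but would accept a transplant. The other is patients who decline RRT but would not describe that as choosing death.

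Item 15 is the only place where a patient states unwillingness to be treated. The introduction (section 1.6) raises the possibility that doctors are more reluctant to start RRT in women. Separating patient refusal from doctor reluctance is therefore a main use of this survey. If willingness to accept a transplant differs by sex, the reported percentages could show a sex difference in one quantity when the reader takes them for another, or hide one. Since forms come back anonymously, an unclear answer cannot be followed up.

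**Working it through.** The plan gives no figure for this item, so there is none to reproduce. The check has two parts.

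**1. Reading the items against each other**

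All doctor questions (1 to 14) and patient items (1 to 17) were read for refusal measures and for the scope of RRT.

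- Patient-reported refusal: item 15 only. Items 10 and 12 to 14 record what the patient was told; item 11 records vascular access.
- Doctor-reported refusal: question 11, with question 12 covering shared decisions not to treat.

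Three types of patient, set against the two sentences of item 15:

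| Patient | RRT not an option | Death rather than dialysis |
|---|---|---|
| Refuses dialysis and transplant, accepts the wording on dying | agrees | agrees |
| Refuses dialysis, would accept a transplant | disagrees | may agree |
| Refuses all RRT, does not see it as preferring death | agrees | disagrees |

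Only the first type can answer without error. With no printed options, a blank may mean disagreement, partial agreement or a skipped item. Counting forms handed out and returned measures non-return of the whole form; it does not resolve a blank on one item.

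**2. Size, as an illustration**

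All inputs are assumptions; none is in the documents.

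- d = 15%: share refusing dialysis, the same in men and women.
- t = 8% of men and 3% of women: share of all patients who refuse dialysis but would accept a transplant.
- The third type of patient in the table is left out.
- p: the fraction of the transplant-accepting group who endorse item 15, taken as equal in both sexes.

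Observed percentage = d − (1 − p) × t.

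Observed difference, women minus men = (1 − p) × (8 − 3) = (1 − p) × 5 points.

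| How the item is read | Men | Women | Difference |
|---|---|---|---|
| As dialysis refusal (p = 1) | 15% | 15% | 0 |
| Half endorse (p = 0.5) | 15 − 4 = 11% | 15 − 1.5 = 13.5% | 2.5 points |
| As refusal of all RRT (p = 0) | 15 − 8 = 7% | 15 − 3 = 12% | 5 points |

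Both ends are correct answers to different questions: in this scenario the true sex difference is 0 for dialysis refusal and 5 points for refusal of all RRT. The defect is that the data do not show which was measured. The upper end equals the sex difference in t. It is 0 if t is the same in both sexes, and it changes direction if the two values of t are exchanged (12% of men v 7% of women).

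**The case against.** The strongest reply is that item 15 can be read literally as a conjunction. A patient who wants a transplant but not dialysis then simply does not agree, and apart from the clause on dying the item returns refusal of all RRT. Further, the analysis is descriptive, no test or endpoint rests on this item, and objective 3 in section 2 is worded around hemodialysis initiation, so dialysis refusal is itself a legitimate target. The timetable (section 3) includes questionnaire development and testing, and missing answer options are not peculiar to item 15: item 6 and the unnumbered statement after item 14 also lack them.

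Much of this is fair, and it limits the point. It does not remove it. Nothing on the form tells patients to use the conjunctive reading. That the plan names both hemodialysis and RRT initiation as its subject is a reason to measure the two separately. A descriptive percentage of unclear meaning stays unclear. Testing might catch the wording, but no revised wording is given.

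Three stronger readings are tempting and are not supported:

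- A reader might infer that the survey has no other measure of refusal. It has: doctor question 11 counts refusals by sex. That question is no substitute, since it is a doctor-reported count at clinic level, limited to 2016 and to refusals against advice.
- A reader might infer that the affected patients cannot respond at all or are forced into a false answer. They can mark the item or leave it; the answer just cannot be interpreted.
- A reader might take 15% v 7% from the illustration and claim a spurious 8-point difference where the truth is zero. That needs every transplant-accepting patient of one sex to endorse the item and every such patient of the other sex not to. It also treats the truth as zero, which holds for dialysis refusal but not for refusal of all RRT.

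**Conclusion.** The point stands as a defect in the wording of one item. The only patient-reported refusal measure mixes two quantities that the survey itself distinguishes, and its result by sex cannot be assigned to either. It also cannot be set cleanly beside doctor question 11: on the scope of RRT in question 9, a patient willing to have a transplant is not an RRT refuser, yet may endorse item 15.

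The actual size is unknown. Under the assumed inputs and equal response behaviour in both sexes, the ambiguity is worth 0 to 5 points in the observed sex difference. Those inputs show the mechanism and are not an estimate. The loss is confined to this item and leaves the rest of the survey intact. It bears on the patient side of the stated hypothesis and cannot be repaired once the forms are returned, so it is worth correcting beforehand.

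**What to change.** Before the questionnaire is distributed, replace item 15 with two items with printed options:

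- *I would accept dialysis (HD or PD): yes / no / undecided.*
- *I would accept a kidney transplant: yes / no / undecided.*

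Drop the clause on dying, or make it a separate yes/no item.

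In the statistics paragraph of section 2.3, state that two results will be reported by sex: dialysis refusal (no to dialysis) and refusal of all RRT (no to both). Show undecided as its own category, and do not merge it with either answer. Refusal of all RRT is then the figure to set beside doctor question 11, with the remaining differences in respondent, year and population noted.

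This is a cheap improvement. It adds one or two lines to the form, fits the development and testing step already in the timetable, and needs no change to sites, sample or type of analysis.

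### Recording only the sex of questionnaire recipients means age-related non-response in the crude percentages for men and women can be neither seen nor corrected

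*Combined protocol and SAP*

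**What the plan says.** Section 2.3 of the combined protocol and SAP states the hypothesis of sub-study 3: "There are sex-specific differences in decision-making of doctors and patients with end-stage renal disease with regards to renal replacement therapy initiation". Sex is therefore the comparison variable.

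The Methodological Note after the patient questions describes the fieldwork:

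- **Who gets a form:** "The questionnaire will be handed out to all patients coming to the outpatient clinic in the year 2017 by non-medical (administrative) personnel".
- **Response check:** "The number of returned questionnaires will be counted and compared to the number of questionnaires that was handed out".
- **What is known about recipients:** "Only the sex of the patient receiving the questionnaire will be recorded".
- **How forms come back:** "The return of the questionnaire will be anonymous, by placing a box in the patient waiting area".

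The returned form asks sex (patient item 1) and age (patient item 2). The statistics paragraph says "Descriptive analysis and graphical illustrations will be performed". It mentions no age stratification, non-response weighting or sensitivity analysis. For sub-study 3 the plan gives no expected response rate, target number of forms or effect size.

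**The concern.** The only thing known about a patient who takes a form and does not return it is the variable being compared. The plan can therefore say what share of men and of women responded, but not which men and which women.

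Age is the obvious worry. It could plausibly affect both the return of a form and the answers that carry the patient-side hypothesis: being told that renal replacement therapy (RRT) is likely, being informed of the options, and regarding RRT as not an option (items 10 and 12 to 15). If older women return fewer forms than older men, the crude percentages shift by different amounts in the two sexes. A real gap can shrink or grow, and the response rates by sex would not reveal the mechanism.

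The denominator has a further gap. Coverage is measured against forms handed out, so an attender who was never offered a form is not counted.

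**Working it through.** The plan states no figure to reproduce. The check is one line of algebra and an illustration.

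**1. Why sex alone cannot correct the crude percentages.** Among returned forms in sex *s*, let *n* be the number returned, *y* the number giving a certain answer and *r* the response rate. Each form gets weight *w* = 1/*r*, the same for all forms of that sex. The weighted percentage is (*w* × *y*)/(*w* × *n*) = *y*/*n*. The weight cancels, so the difference, ratio and odds ratio between the sexes are unchanged.

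**2. Illustration with age. All rates are assumptions.**

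- Aged 75+: 25% of male and 40% of female attenders.
- Informed about an option: 45% under 75 and 25% at 75+, the same in both sexes.
- Response: 60% under 75 in both sexes; at 75+, 45% in men and 25% in women.

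True crude percentages:

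- Men: 0.75 × 0.45 + 0.25 × 0.25 = 40.0%
- Women: 0.60 × 0.45 + 0.40 × 0.25 = 37.0%
- Gap: 3.0 points

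Share of recipients who respond:

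- Men: 0.75 × 0.60 + 0.25 × 0.45 = 0.45 + 0.1125 = 0.5625
- Women: 0.60 × 0.60 + 0.40 × 0.25 = 0.36 + 0.10 = 0.46

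Crude percentages on returned forms:

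- Men: (0.45 × 0.45 + 0.1125 × 0.25)/0.5625 = 0.2306/0.5625 = 41.0%
- Women: (0.36 × 0.45 + 0.10 × 0.25)/0.46 = 0.187/0.46 = 40.7%
- Gap: 0.3 points

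The planned check would report response of 56% in men and 46% in women. By step 1, these two rates leave the 0.3 as it is.

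**3. Other response patterns, all else equal.**

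| Response at 75+ (men / women) | Men | Women | Gap |
|---|---|---|---|
| 45% / 25% | 41.0% | 40.7% | 0.3 points |
| 35% / 35% | 0.2244/0.5375 = 41.7% | 0.197/0.50 = 39.4% | 2.3 points |
| 25% / 45% | 0.2181/0.5125 = 42.6% | 0.207/0.54 = 38.3% | 4.2 points |

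The third row is the first with the sexes exchanged: men 0.45 + 0.25 × 0.25 = 0.5125, women 0.36 + 0.40 × 0.45 = 0.54. Against a true 3.0, the observed crude gap can be too small or too large.

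**4. Within age groups.** Response here depends only on sex and age, so each age-specific percentage on returned forms is right: 45% and 45% under 75, 25% and 25% at 75+. An age-standardised contrast is 0 whatever the response rates. The 3.0-point crude gap comes wholly from the older age mix of the women.

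**5. What sex-by-age counts add.** Weighting each cell back to its recipient count restores 40.0% and 37.0%, again because response depends only on sex and age.

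**6. What they do not add.** Suppose 20% of each sex hold a view and men respond at 50% regardless. Women respond at 30% if they hold it and 55% if not. Overall response in women is 0.20 × 0.30 + 0.80 × 0.55 = 50%, equal to men. Observed prevalence in women is 0.06/0.50 = 12% against 20% in men, a spurious difference of 8.0 points. If this pattern holds within each age band, weighting by age leaves it in place. Equal response by sex is therefore no reassurance either.

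**The case against.** The strongest objection is that the illustration harms only the crude contrast. The form asks age, so age-specific or age-standardised comparisons can be made from returned forms alone, and in the illustration they are unbiased. For the question whether clinics inform women and men differently, the age-standardised value of 0 is arguably more relevant than the crude 3.0. Making the weighted crude percentages the main result would put an age-mix difference in front. This stands. It limits the point to the crude percentages and decides which analysis should lead. It does not remove the point: the plan states no age-stratified analysis, and such an analysis would not show coverage by age or restore the overall percentages.

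Second, the plan does not promise a correction. It describes a count comparison in a descriptive sub-study. This also stands: the point is an unaddressed limitation, with no contradiction or arithmetic error.

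Third, other information exists. Response rates by sex allow worst-case bounds, although the range for a difference is 2 × (1 − *r*) wide, or 100 points at 50% response in both sexes. They also matter for pooled estimates and for the share of women among those giving an answer. Doctor items 4 to 8 overlap patient items 10 to 14. They are clinic totals reported by doctors and built around 2016 registrations, while the patients attend in 2017, and no calibration is planned. They offer a rough comparison at most.

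A reader might infer that no comparison of men and women from this survey can be rescued. The documents do not support that, because sex and age are both on the returned form.

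**Conclusion.** The point holds for the crude percentages of men and women. As written, the plan can report response by sex, but it can neither show nor correct age-related non-response in those percentages. The illustrated size is a true crude gap of 3.0 points seen as 0.3, with 2.3 and 4.2 under the other two patterns. All of these rest on assumed age mixes, answer rates and response rates. They show what could happen and do not estimate the bias in this survey.

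It would go too far to conclude that the survey's sex contrasts are biased, or that its findings cannot be used. Nothing in the documents says how response varies with age, and within-age contrasts are sound if response depends only on sex and age. I would class this as a cheap improvement.

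**What to change.** 1. At handout, tick an age band next to sex (for example under 50, 50–64, 65–74, 75+). Alternatively, obtain one aggregate table per clinic of unique attenders by sex and age band. The clinic table also counts attenders who were never offered a form.
2. Report response, or coverage of attenders, for each sex-by-age cell.
3. Present age-specific or age-standardised contrasts between men and women, using patient item 2 and a standard age distribution fixed in advance.
4. Show the crude percentages weighted to the sex-by-age counts as a sensitivity analysis beside the unweighted ones.
5. State that none of this removes non-response that depends on the answer itself within an age band.
6. Make the counts match the actual collection period, since section 2.3 mentions both three months of collection and the year 2017. Set a rule for repeat attenders: patient item 9 allows for visits at least three times a year, and anonymous returns cannot be de-duplicated afterwards.

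The cost is one extra tick per form or one table per clinic, some added analysis, and a slight loss of precision from weighting. Aggregate counts in coarse bands keep the returned forms anonymous.
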